## 5.4 Description of the study procedure

Following the baseline visit including randomization (see 5.3), patients will receive active treatment or control (fNIRS neurofeedback/EEG neurofeedback) or delayed treatment which involves a period of 8 weeks without treatment. If a patient was randomized into the delayed treatment condition, the following variables will be assessed prior to the treatment 8 weeks after randomization:

Time point	Variable
Only delayed treatment  Before start of therapy Week 8 (+ max. 2 weeks)	
 
Anamnesis
 
Comorbidities
 
Medication intake
 
Anthropometry
 
Sociodemographics
 
Eating disorder psychopathology e.g., Eating Disorder Examination (EDE)
 
General psychopathology e.g., Patient Health Questionnaire (PHQ)
 
Neuropsychological and brain activity-related measures e.g., Go/NoGo task
 
Behavioral measures e.g., Bogus taste test
 
Visual analogue scales (VAS): expectations, motivation
 

During treatment, all patients will be assessed weekly (i.e. at each treatment session), including the following variables:

Time point	Variable
During treatment, weekly Active treatments: Weeks 1-7 Delayed treatment: Weeks 9-15	
 
Brain activity-related outcomes e.g., EEG frequency band power
 
Visual analogue scales (VAS): state craving, liking, sense of control, hunger, satiety, and mood
 
Objective binge-eating episodes
 
(Serious) adverse events
 

The following variables will be assessed at the end of treatment, 8 (fNIRS neurofeedback and active control treatments) or 16 (delayed treatment control condition) weeks after randomization.

Time point	Variable

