### 7.4.2 Statistical error terms

The level of significance is set at  $\alpha = 5\%$ , aiming for a power of  $1 - \beta = 80\%$ .

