### 7.4.4 Sample size calculation

Based on a conservative effect size of 0.55 (compared to 0.65 quoted above), a t-test will have 80% power if 63 patients are analyzed (42 in the pooled intervention groups and 21 in the waiting control group), as determined using the software PASS 11. The width of the confidence intervals for the difference in means between two groups can then be expected to be about 0.88 SD for the pooled variance. The covariates incorporated into the analysis methods mean that the true power can be expected to be somewhat higher than that of the t-test reported here.

Taking into account a drop-out rate of about 20%, a total of 78 patients (26 per group) will be randomized.

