### 2.3 Further variables

Control variables at baseline (T0) are used to characterize the patients and may be relevant for outcomes, so that particular attention is warranted to ensure that random differences between the groups are not large.

- Vigilance: Perception and attention functions battery (WAFA), log-transformed mean reaction times in ms, measure of dispersion (variability in performance in intrinsic and phasic vigilance) in ms
- Intelligence: Raven's Coloured Progressive Matrices, number of correct responses, age- and sex-specific percentile rank
- Working memory: N-back task, number of correct responses, age- and sex-specific percentile rank

Variables that may be relevant for session-wise and overall neurofeedback outcomes assessed in each session:

- Helpfulness of the training: general (PRE31), related to eating behaviour (PRE32), to relax (PRE33), scale between 0-6
- Questions about strategies: Attempts to apply strategies in daily life during the past seven days (PRE41), success in applying the strategies used during training (PRE42), success in applying these strategies related to eating behaviour (PRE431) and to relax (PRE432)
- PHQ-15: sum score (variables PRE51 – PRE515)
- Strategies that were used for the session (POST21), reported in an exemplary fashion (Item 3c of the CRED-nf checklist)
- Success in regulating brain activity during the past session (POST22), scale between 0-6

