### 4.1 Primary endpoint

The primary endpoint, the number of OBEs at post-assessment or post-waiting, will be analysed using ANCOVA with OBEs as the dependent variable, OBEs at T0 as a covariate as well as the stratification criteria (`strabmi`, `stralsex`, `strawei`). The code for this test will have the structure

```
anova(lm(OBE_FU ~ OBE_T0 + STRABMI + STRASEX + STRAWEI + ARMS)).
```

The variables OBE\_FU and OBE\_T0 will be shifted by the mean of OBE at T0 so that the intercept in the model reflects change in time. A closed-testing procedure will be used, meaning

---

 The planned dates are as follows: session 1/2 (week 1), session 3/4 (week 2), session 5/6 (week 3), session 7/8 (week 4), session 9 (week 5), session 10 (week 6), session 11 (week 7), session 12 (week 8),

that the initial comparison will be between the two intervention groups combined and the waiting group and the three pair-wise tests (fNIRS vs. wait control group, EEG vs. wait control group and fNIRS vs. EEG group) will be performed without adjustment if the global test is significant. If the global test is not significant, estimates and confidence intervals will still be provided for the contrasts in OBE, but no formal statistical test will be carried out. Estimates will be taken from the linear model and a Wald confidence interval will be used. Moreover, secondarily, the analogous analysis with effect size will be performed.

Missing data will be treated with multiple imputation using the R package “mice” (van Buuren and Groothuis-Oudshoorn 2011). The imputation variables will include the answer to the question “In how many of the situations in which you ate too did you feel you had lost control of your eating behaviour” (pre72). Sex, BMI and the stratification variable participation in a weight-loss programme will also be used. Fifty imputations will be performed.

To test the robustness of the results, the primary analysis will be repeated without imputation and pessimistic and optimistic scenarios will be considered.

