### 4.2.2 Analysis of continuous variables

Mean and SD will be provided at all available points in time for all valid values and after imputation. Imputation variables will include all data from the same “category” of secondary endpoints along with age and sex. If the imputation methods should fail to converge, then imputation variables will be successively removed starting with those having the weakest absolute value for linear correlation.

Variables at T1/T0WL will be analysed with linear models having the same structure as for the primary endpoint, but will include all three randomization arms from the outset (i.e. will not make use of the closed testing principle). Here too the variables will be shifted as with the primary endpoint.

Data for T0, T1 and T2 will be analysed for the intervention groups in a mixed model in which the stratification variables, time and group will be treated as fixed effects including the interaction between group and time. The patient ID will be treated as a random term. The model will be fit using restricted maximum likelihood (REML) and an unstructured variance-covariance matrix.

If multiple sub-scales of a questionnaire are tested formally, then Bonferroni-Holm correction for multiplicity will be used.

---

 The original German reads „In wie vielen dieser Situationen, in denen Sie zu viel gegessen haben, hatten Sie das Gefühl, die Kontrolle über Ihr Essverhalten verloren zu haben (während des Essens)?“

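### The imputation variables named for the primary endpoint omit randomised arm and baseline OBEs; used alone, they would bias the neurofeedback effect towards zero

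*SAP*

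**What the plan says.** SAP 4.1 takes OBEs at T1 (active arms) or T0WL (waitlist) as the outcome of an ANCOVA with OBE_T0, the three stratification factors and ARMS. The pooled neurofeedback-versus-waiting contrast is tested first, and the three pairwise tests are carried out only if it is significant.

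Missing data are handled by mice with 50 imputations. Protocol 7.5.2 had reserved imputation for missing data expected to cause meaningful bias; in the SAP it is the standard treatment. On its content the SAP says: "The imputation variables will include the answer to the question" about losing control when overeating (pre72), and then: "Sex, BMI and the stratification variable participation in a weight-loss programme will also be used". It does not mention arm or OBE_T0, and it gives no predictor matrix, imputation method or by-arm rule. A repeat without imputation, and pessimistic and optimistic scenarios, are planned as robustness checks.

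For continuous secondary endpoints, SAP 4.2.2 imputes from all data in the same category "of secondary endpoints along with age and sex". If imputation does not converge, variables are removed one by one, weakest linear correlation first.

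The SAP does not say when pre72 is collected. SAP 2.3 lists other items with the PRE prefix under "Variables that may be relevant for session-wise and overall neurofeedback outcomes assessed in each session". Protocol 5.4 says "During treatment, all patients will be assessed weekly (i.e. at each treatment session), including the following variables" and places these assessments in weeks 9 to 15 for delayed treatment, after the week-8 visit that supplies the waitlist endpoint.

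**The concern.** An imputation model should contain every term of the analysis model. If arm is left out, a missing outcome is drawn from a mixture of the arms, so the completed data understate the difference under test. If baseline OBEs are left out, the draws lose their link to the strongest routine covariate.

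This affects the primary result. The pooled contrast is the gate for all formal pairwise testing, so an attenuated estimate there can prevent the fNIRS, EEG and waiting arms from being formally compared at all.

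The main auxiliary variable adds to the concern. If pre72 is asked only at therapy sessions, it does not exist for the waitlist before T0WL. Then mice would either fill it in from relations seen in the active arms or use values recorded after the endpoint. The SAP does not say which.

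**Working it through.** **The plan's own figure.** Protocol 7.4.2 states: "The level of significance is set at" 5%, with sidedness not given. Protocol 7.4.4 reads: "Based on a conservative effect size of 0.55 (compared to 0.65 quoted above"), and then "a t-test will have 80% power if 63 patients are analyzed" (42 versus 21). The noncentrality is 0.55 / √(1/42 + 1/21) = 0.55 / 0.267 = 2.06 on 61 degrees of freedom. Power is then 53% two-sided or 65% one-sided, so the 80% does not reproduce as a plain t-test. That is a separate matter. Here 0.55 SD serves only as the effect size, and the stated 80% is not used as a benchmark.

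**Inputs.**
- 78 randomised, 26 per arm, hence 52 versus 26 for the pooled contrast (Protocol 7.4.4).
- 20% dropout (Protocol 7.4.3), taken as the upper end for missing outcomes.
- Assumed: 5% and 10% as lower missing fractions; outcomes missing completely at random; baseline–outcome correlation 0.5; correlation of a pre72-like item with the outcome 0.4 or 0.6.

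**Closed form, arm absent and no informative auxiliary.** Let f and g be the missing fractions in the pooled active and waiting arms, and p the active share of observed patients. An imputed outcome has expectation p·μA + (1 − p)·μW in either arm. The completed-data difference is then

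δ·[1 − f(1 − p) − g·p],

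which reduces to δ·(1 − f) when f = g.

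- 5%: 0.55 × 0.95 = 0.52
- 10%: 0.55 × 0.90 = 0.50
- 20%: 0.55 × 0.80 = 0.44
- 20% active, 10% waiting: p = 0.64, factor 1 − 0.072 − 0.064 = 0.864, giving 0.48
- 10% active, 20% waiting: factor 0.831, giving 0.46
- 30% active, 10% waiting: factor 0.822, giving 0.45

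**Simulation.** 600 runs per setting, true effect 0.55, 50 Bayesian linear imputations, Rubin's rules, two-sided 5%. Ranges cover the two pre72 settings, which are separate sets of runs. Entries are mean effect (power).

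| Imputation predictors | 10% missing | 20% missing |
|---|---|---|
| Sex, BMI, programme | 0.50–0.51 (54–57%) | 0.42–0.43 (34%) |
| Those plus pre72-like item, available for everyone | 0.52 (60–61%) | 0.44–0.47 (40–47%) |
| Sex, BMI, programme plus OBE_T0, no arm | 0.50–0.51 (58–63%) | 0.43 (37–41%) |
| Sex, BMI, programme plus OBE_T0 and arm | 0.56–0.57 (68–72%) | 0.54 (57–59%) |
| Complete-case ANCOVA | 0.56–0.57 (68–72%) | 0.54 (57–60%) |

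The last two rows should both return 0.55, so simulation error is about 0.01 to 0.02. Adding OBE_T0 without arm leaves the estimate where it was and improves only power. Adding arm as well removes the bias. An informative pre72 measured in everyone, the favourable case, recovers only part of the loss.

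**Timing of pre72.** Its prefix matches the session items in SAP 2.3, although pre72 itself is not listed there. Session assessments for delayed treatment begin in week 9, and the waitlist endpoint is at week 8. If pre72 is a session item, no waitlist patient has a value before the endpoint.

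**The case against.** The strongest reply is that the SAP does not exclude arm or OBE_T0. It says what the variables will include, never calls the list complete, and mice uses every column supplied unless told otherwise. A reader might infer that the planned imputation certainly shrinks the effect. The documents do not support that: they are silent, and the shrinkage follows only if the named variables are the whole model. This stands, and it makes the finding conditional. It does not remove it, because the same text permits both a biased and an unbiased primary estimate.

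Other replies also stand:

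- **pre72.** That it is wholly missing for the waitlist is an inference from a variable name. A waitlist patient who missed T0WL but began therapy could have a value soon afterwards, though one lost earlier probably would not.
- **Missing fraction.** Twenty per cent with an uninformative pre72 is a worst case. Protocol 5.6.1 and 7.4.3 keep assessing patients who stop treatment. SAP 3.1 removes from the full analysis set controls who could not attend T0WL because of SARS-CoV-2, and requires T1 data from active patients whose intervention was cut short for that reason.
- **Secondary endpoints.** A reader might infer that baseline values are ignored there too. Same-category data recorded from T0 to T2 naturally cover them, and removal applies only on non-convergence. What remains unnamed is arm and the stratification factors other than sex.
- **Safeguard.** The repeat without imputation would expose the problem; complete-case ANCOVA matched the corrected imputation above. But it is a robustness check and does not replace the result that opens or closes the gate.
- **Direction.** The bias is towards no effect, so the risk is lost power, not a false claim of efficacy.

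**Conclusion.** The point holds in conditional form. SAP 4.1 names secondary predictors for the primary imputation and leaves out the tested term and the baseline covariate. Run as listed, it would multiply the pooled effect by roughly one minus the fraction imputed: 0.55 SD becomes about 0.52 at 5%, 0.50 at 10% and 0.42 to 0.47 at 20%, the last range depending on how informative and available pre72 is. At 20% missing, simulated power is 34% to 47%, against 57% to 59% with arm and OBE_T0 included. Arm accounts for the bias; OBE_T0 mainly affects precision.

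These sizes rest on outcomes missing completely at random, a baseline correlation of 0.5 and missing fractions that the documents do not give. Only the pooled contrast was simulated. The plan states no fNIRS-versus-EEG effect, so no size is claimed for that comparison.

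**What to change.** In SAP 4.1, state that the imputation model always contains randomised arm at three levels (or that imputation is done by arm), OBE_T0 and the three stratification factors. Sex, BMI and programme participation are already named, so the new content is arm and OBE_T0. Give the predictor matrix and the imputation method.

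State when pre72 is collected, and use it only where it is measured before the endpoint, for example as an auxiliary within the two active arms.

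In SAP 4.2.2, add arm and the stratification factors to the imputation variables, and exempt them and the baseline value of the endpoint from removal on non-convergence.

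The cost is a few sentences and an edit to the mice predictor matrix, with no new data. If this was always intended, the change is a clarification.

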## 4.2 Secondary endpoints

### 4.2.1 Analysis of binary variables

Abstinence from objective binge eating and remission as defined above will be compared between randomization arms at T1/T0WL using an exact Fisher test and presenting the proportion of patients abstinent/in remission per arm with a Wilson confidence interval. In addition, a logistic regression with the stratification variables and categories for the number of binge-eating episodes at baseline (0, 1–3, 4–7, 8–13, >13) as covariates will be performed. If the model converges, odds ratios for the difference between arms will be taken from the coefficients and confidence intervals using a profiling method. If there are problems with convergence, then the number of categories in the covariates will be reduced and, if need be, covariates will be removed.

The abstinence from binge eating and remission from BED data at T2 for the intervention groups and end of treatment for the control group will be presented, but no formal statistical test will be performed.

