### 7.4.3 Drop-outs

A drop-out rate of 15% was observed in an EEG neurofeedback trial with a follow-up 3 months after end of treatment. Based on these data and our own experience we assume a dropout rate of 20%. Although dropped-out from treatment, patients who discontinued treatment will be assessed at later assessment time points, if possible.

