## 3 General analysis definitions

### 3.1 Analysis populations

Analysis of the primary and secondary outcomes are based on the full analysis set (FAS). Note that patients fulfilling the criterion for abstinence at T0 will not be included in the analysis for this endpoint. Further, the analysis of the primary outcome will be performed in the per-protocol set (PPS) to evaluate the treatment effect for patients with good protocol adherence, if FAS and PPS comprise a sufficiently different set of patients. Analysis of the fNIRS data will be performed in the fNIRS data set.

The FAS includes all randomized patients unless purely technical issues precluded the fNIRS measurements. In particular, three patients had to be replaced because of the aforementioned technical issues with fNIRS. Patients who could not complete the intervention due to the SARS-CoV-2 situation will be retained in the FAS if they completed at least 5 sessions and provided OBE data at T1. In control patients, those who could not attend T0WL due to SARS-CoV-2 will not be retained in the FAS.

The PPS includes all patients of the FAS without serious violations of the study protocol. The following protocol violations are classified as serious:

- Violation of at least one inclusion or exclusion criterion

- Treatment was not conducted as mandated, that is
  - Temporal delay of last attended treatment session by 4 weeks relative to the planned date, `exdat`, (based on the date of the first treatment session). Note that consideration of a maximum of two weeks' delay in each session as originally foreseen was not considered feasible.
  - Absence of more than 6 of the planned 12 treatment sessions (based on `meet`)
- Use of forbidden medication
- Psychological treatment during study participation (was not the case, otherwise it would be documented in the "comments")

The fNIRS/EEG data set includes all patients from the fNIRS/EEG group of the FAS who provided data for more than a single neurofeedback session. Participants with fewer sessions are excluded from the analyses, because the definition of neurofeedback *training* does not apply for these participants and there is no information on between-session variability.

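### The fallback for the adjusted abstinence and remission model does not cover an arm with zero events, and R's convergence flag would usually not reveal it

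*SAP*

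**What the plan says.** SAP 4.2.1 compares abstinence and remission between arms at T1/T0WL with Fisher's exact test and gives each arm's proportion with a Wilson interval. As an addition, it fits a logistic regression on arm, the three stratification variables and "categories for the number of binge-eating episodes at baseline", of which it lists five, starting with zero. Odds ratios and profile intervals are taken from this model on the condition that it converges. Otherwise "then the number of categories in the covariates will be reduced and, if need be, covariates will be removed". The section plans no check for separation and names no method for an arm in which nobody, or everybody, has the event.

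SAP 3.1 adds that "patients fulfilling the criterion for abstinence at T0 will not be included in the analysis for this endpoint", the endpoint being abstinence. Protocol 7.4.4 states that "a total of 78 patients (26 per group) will be randomized" and bases its power on "42 in the pooled intervention groups and 21 in the waiting control group". Neither document gives an expected abstinence or remission rate for any arm.

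**The concern.** Maximum-likelihood logistic regression has no finite solution when a covariate pattern predicts the outcome perfectly (separation). The SAP's rule deals with separation that comes from the covariates. It does not deal with separation that comes from the arm term, which is the one term the model exists to estimate and which cannot be removed.

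The trigger is also weak. Fitting software stops when the likelihood stops improving, and under separation that happens while the coefficient is still drifting to infinity. A converged flag therefore does not show that the odds ratio is usable. At stake are the adjusted odds ratios against waitlist, the only adjusted effect sizes planned for these two endpoints. They would fail in the very data set that most favours treatment over waiting.

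**Working it through.** **Plan's own figure.** SAP 4.2.1 states none. The only design figures used here are the waitlist sizes in Protocol 7.4.4: 26 randomised and 21 analysed (26 × 0.8 = 20.8, with the 20% drop-out of Protocol 7.4.3).

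**1. Number of parameters.**
- Abstinence: baseline category zero is empty because of the exclusion in SAP 3.1, leaving four categories. Intercept 1, strata 3, baseline 3 and arm 2 make at most 9.
- Remission: that exclusion does not apply. Intercept 1, strata 3, baseline 4 and arm 2 make at most 10.

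**2. An empty arm cell.** With 0 of n waitlist events, the odds of the event on waitlist are estimated as zero, so any odds ratio with waitlist as reference is infinite. Other covariates do not alter this as long as arm is in the model. Simulated trials were checked by linear programming for separation (21 per arm, waitlist rate 2% to 20%, active rate 20% or 30%, invented covariate mixes, 1,000 trials in each of ten scenarios). In all 2,218 trials with no waitlist event, the full, the collapsed and the arm-only models were separated. An R-type fit nevertheless met its convergence criterion in 2,217 of them.

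**3. Example in R (version 4.3.3).** Events 0/21 waitlist, 6/21 fNIRS, 5/21 EEG; arm only, so every covariate has already been removed.

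| Quantity | Result |
|---|---|
| Convergence flag | TRUE |
| Log odds ratio, fNIRS vs waitlist | 18.65 (SE 2,347) |
| Odds ratio | exp(18.65), about 1.26 × 10⁸ |
| R profile limits, log scale | −212 and NA |
| Odds ratio, fNIRS vs EEG | odds 6/15 = 0.40 divided by odds 5/16 = 0.3125 gives 1.28, finite |
| Fisher's test, three arms | p = 0.030 |
| Wilson interval for 0/21 | 0 to 15.5%, the upper limit being 3.84 divided by 24.84 (21 plus 3.84) |

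The lower limit that R returned is an artefact too: solving the profile likelihood directly gives a lower limit of about 3.4 for the odds ratio, with no upper limit. A second fit with two invented covariates added behaved in the same way: converged, log odds ratios of 17.8 and 18.5, upper limits missing.

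**4. Probability of an empty waitlist cell.** P(0 events) = (1 − p)ⁿ, where p is assumed:

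| Assumed p | n = 21 | n = 26 |
|---|---|---|
| 2% | 65% | 59% |
| 5% | 34% | 26% |
| 10% | 11% | 6.5% |
| 15% | 3% | 1.5% |
| 20% | 0.9% | 0.3% |

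Setting (1 − p)ⁿ to one half and solving for p shows that it exceeds 50% only if p is below 3.3% (n = 21) or 2.6% (n = 26).

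**5. Where the existing rule works.** At least one waitlist patient had an event but the full model was still separated in 6% to 28% of trials, depending on the scenario. Dropping covariates cured 90% to 100% of these.

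**6. Firth on the same example.** For an arm-only model the penalty amounts to adding 0.5 to each cell. The fNIRS odds become 6.5/15.5 = 0.4194 and the waitlist odds become 0.5/21.5 = 0.02326, so the odds ratio is 18.0. The 95% penalised-profile interval is 1.9 to about 2,400. This was not run with the full covariate set.

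**The case against.** The strongest reply is that little depends on this model. It supplements Fisher's test and the Wilson intervals, which both handle an empty cell and show the size of the contrast between arms. Protocol 7.5.2 treats the secondary outcomes as exploratory, and the primary analysis is untouched. An analyst who saw an odds ratio of 126 million would not publish it. All of that stands and limits the consequence. It does not repair the rule: the SAP makes convergence the condition for reporting, and it leaves the analyst to improvise once the data are known.

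A second reply is that an empty cell may well not occur. One waitlist event removes it, so few events are not enough. Low-frequency BED is eligible (Protocol 4.1), and the SAP itself foresees patients with no episodes at T0, which makes some untreated zeros plausible. In the other direction, the 28-day window makes a zero count harder to reach, and the exclusions in SAP 3.1 can reduce the waitlist denominator. The documents do not settle which effect is larger.

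A reader might also count every separated fit as a failure of the plan. In the simulations with waitlist rates of 5% to 10%, separation somewhere in the full model occurred in 21% to 57% of trials. That figure includes separation from sparse baseline categories, which the existing rule mostly cures. An empty waitlist cell accounted for 9% to 35%.

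**Conclusion.** The gap is real and narrow. With no events in an arm, the odds ratios against that arm are infinite, no step in SAP 4.2.1 can change this, and R will usually report convergence, so the fallback would not be triggered. Followed literally, the plan would then report a meaningless odds ratio and profile interval.

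A reader might infer that this is likely, or that all the planned odds ratios are at risk. The documents support neither. For assumed waitlist rates of 5% to 10% the probability of an empty waitlist cell is about 11% to 34% with 21 analysed and 6.5% to 26% with 26; at 20% it is about 1% or less. These figures rest wholly on the assumed rates and apply to abstinence or remission alike, since neither rate is given. The fNIRS versus EEG odds ratio stays finite, and Fisher's test and the Wilson intervals remain valid.

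**What to change.** In SAP 4.2.1:

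- Replace the convergence condition with an explicit check for separation, including a zero or full cell in any arm.
- State that, when separation is present, the adjusted odds ratios come from Firth-penalised logistic regression with profile penalised-likelihood intervals and the planned covariates retained. The covariate set then no longer depends on the data.
- For abstinence, drop the empty zero category from the list of baseline categories.
- Keep Fisher's test and the Wilson intervals as they are.

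Replacing the baseline categories with a continuous term such as log(1 + OBE) is optional and not needed for this repair.

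The cost is a short SAP edit and one R package. The odds ratios are shrunk slightly, and with an empty cell the interval will be very wide, as the example shows, but it is finite and specified in advance.
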